#### *1.2.1.3 Pharmacokinetics*

A pharmacokinetic (PK) study in male rats, by administering single intravenous (IV) injection of 5 mg/kg KM-819 showed:  $C_{max}$ : 62.73 ug/ml,  $t_{max}$ : 0.083 hr, and  $t_{1/2}$ : 7.08 hr. Single dose oral administration of 5 mg/kg KM-819 resulted in:  $C_{max}$ : 3.89 ug/ml,  $t_{max}$ : 3 hr, and  $t_{1/2}$ : 6.06 hr. Oral bioavailability assessed by comparing  $AUC_{0-\infty}$  for oral and IV administration was 35.97%.

A PK study in male dogs, by administering single IV injection of 1 mg/kg KM-819 showed:  $t_{max}$ : 0.08 hr,  $C_{max}$ : 11.91 ug/ml, and  $t_{1/2}$ : 8.61 hr. Single dose oral administration of 5 mg/kg and 10 mg/kg KM-819 resulted in:  $t_{max}$ : 0.83 hr and 0.58 hr,  $C_{max}$ : 6.01 ug/ml and 9.48 ug/ml, and  $t_{1/2}$ : 4.96 hr and 5.03 hr, bioavailability: 32.3% and 28.9%, respectively.

In vitro plasma protein binding is 99.96 %, 99.79%, and 99.96% in rat, dog and human, respectively. KM-819 at 10 uM did not inhibit CYP450s (including 1A2, 2C9, 2C19, 2D6, 3A4) and P-gp.

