### **5.3 Rationale for Selection of Starting Dose**

The FDA Guidance “Estimating the Safe Starting Dose in Clinical Trials for Therapeutics in Adult Healthy Volunteers” and allometric scaling modeling and simulation were used for the initial calculation of the starting human dose in this study. Based on the FDA Guidance document and the 4-week rat toxicology study NOAEL of 500 mg/kg/day, the human equivalent dose (HED) is estimated to be 5600 mg for a 70 kg human subject. A 10-fold safety factor is applied to the HED, resulting in an estimated Maximum Recommended Starting Dose (MRSD) was 560 mg per person for a 70 kg person. In addition to the FDA Guidance method, an allometric scaling method was used to predict human PK. The human PK parameters were predicted as followed: CL= 2.93 L/h, V = 39.2 L, and half-life =9.27 hours. Using these predicted human PK parameters, simulation was conducted based on the assumption that human PK behaves with one compartment model with first order absorption and first order elimination rate and the bioavailability was assumed to be 35% (mean F from animal data).

Based on simulated human PK profile and animal efficacy data, a lower dose was chosen for the starting dose.

The first-in-human Phase 1 single ascending dose study will have an initial starting dose of 10 mg, which is x56-fold below the estimated MRSD derived from the rat NOAEL.

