### 6.2 Pharmacokinetic Variables

#### 6.2.1 *KM-819 Pharmacokinetic Blood Sampling*

Blood (approximately 6 mL) will be taken by venipuncture or cannulation of a forearm vein(s) and collected into anticoagulant EDTA K2 tubes. Blood will be processed for plasma by centrifuging at 4°C, 3000 rpm for 10 min. The obtained plasma will be transferred into 3 polypropylene tubes (1.5 mL) with a volume of 0.8 mL, respectively. The tubes will be immediately stored at -70°C freezer. Two aliquots of plasma samples will be transferred to Bioinfra Co., Ltd and be analyzed by a validated method for the concentration of KM-819 (Parts A and B); one aliquot will be stored in study center as a back-up until completion of the clinical study report (CSR).

The PK parameters listed in Section 3.2.2 will be calculated from the plasma concentration-actual time profiles. The non-compartmental analysis will be performed using Phoenix® WinNonlin® Software Version 6.3 or higher (Certara, L.P., [name]).

The total volume of PK blood drawn from each subject will be approximately 72 mL in Part A SAD and 144 mL in Part B MAD.

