### **6.2.3 KM-819 Pharmacokinetic CSF Sampling**

CSF (approximately 2 mL) will be taken by lumbar puncture between the 3rd and 4th lumbar vertebrae. CSF samples will be transferred into 3 polypropylene tubes (1.5 mL) with a volume of 0.5 mL, respectively. The tubes will be immediately stored at -70°C freezer. Two aliquots of CSF samples will be transferred to Bioinfra Co., Ltd and be analyzed by a validated method for the concentration of KM-819 (Part B only); one aliquot will be stored in study center as a back-up until completion of the CSR.

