For graphs of arithmetic means all BLQ mean concentrations will be substituted by zeros. Graphs of geometric means include only time points with minimum concentration greater than zero. Any arithmetic mean that is BLQ will be excluded from log/linear presentation of arithmetic means. Any BLQ values prior to the last quantifiable concentration will be plotted at zero for individual linear/linear graphs and excluded from log/linear graphs. All BLQ values after the last quantifiable concentration will be excluded from individual linear/linear and log/linear graphs.

Handling of values below the limit of quantification (BLQ) in listings and for the calculation of descriptive statistics at each time point:

All concentrations below the limit of quantification (BLQ) or missing data will be labeled as such in the concentration data listings. Missing samples will be reported as no sample ("NS") and excluded from analysis. Values that are BLQ will be substituted with zero for the calculation of descriptive

PAREXEL International

Statistical Analysis Plan

statistics of concentration by time point and will be displayed as “not calculable” or NC for the calculation of statistical summaries.

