6.3.13 Pharmacodynamic Variables

The analysis of the pharmacodynamic (PD) data will be based on the pharmacodynamic population.

In both Parts A and B, mean and absolute value change from baseline at each post-baseline measurements for:

- Bond and Lader Visual Analogue Scale (VAS) [Table 14.2.8.1 (Part A) and Table 14.2.8.2 (Part B)]
- Profile of Mood States (POMS) [Table 14.2.9.1 (Part A) and Table 14.2.9.2 (Part B)]
- Korean Wechsler Adult Intelligence Scale-IV (K-WAIS-IV) [Table 14.2.10.1 (Part A) and Table 14.2.10.2 (Part B)]
- C-SSRS

In Part B only, PD parameters in plasma and CSF including:

- alpha synuclein oligomer [Table 14.2.11]
- total Tau [Table 14.2.12]

PAREXEL International Statistical Analysis Plan

- phospho-Tau [Table 14.2.13]
- Ratio of CSF concentration/Plasma Cmax. [Table 14.2.14]

For Part A and Part B, the PD parameters (Bond and Lader Visual Analogue Scale (VAS) [Listing 16.2.9.4.1 (Part A) and Listing 16.2.9.4.2 (Part B)], Profile of Mood States (POMS) [Listing 16.2.9.5.1 (Part A) and Listing 16.2.9.5.2 (Part B)], Korean Wechsler Adult Intelligence Scale-IV (K-WAIS-IV) [Listing 16.2.9.6.1 (Part A) and Listing 16.2.9.6.2 (Part B)], C-SSRS [Listing 16.2.9.7.1 (Part A) and Listing 16.2.9.7.2 (Part B)],

In Part B only, PD parameters in plasma and CSF including: alpha synuclein oligomer [Listing 16.2.9.8], total Tau [Listing 16.2.9.9], phospho-Tau [Listing 16.2.9.10], Ratio of CSF concentration/Plasma Cmax. [Listing 16.2.9.11]) will be listed within each study part and by cohort and time point and will include both absolute values and changes from baseline. Listing of CSF Concentration of KM-819 will be presented [Listing 16.2.6.3 (Part B)].

The baseline for each of Bond and Lader Visual Analogue Scale (VAS), Profile of Mood States (POMS), Korean Wechsler Adult Intelligence Scale-IV (K-WAIS-IV), alpha synuclein oligomer, total Tau and phospho-Tau parameters will be the Day 1.

Pharmacodynamic data will be summarized using descriptive statistics (n, mean, SD, minimum, median and maximum).

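### The only plasma-normalised CSF measure divides by total, not unbound, plasma Cmax of a 99.96% bound drug, and no rule covers CSF values below the assay limit

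*SAP*

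**What the plan says.** SAP 6.3.13 lists the measure among the Part B pharmacodynamic parameters: "Ratio of CSF concentration/Plasma Cmax", reported in Table 14.2.14. The title of that table promises observed values and change from baseline. The Protocol carries the same endpoint in 3.2.3.

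Plasma is "analyzed by a validated method for the concentration of KM-819 (Parts A and B") under Protocol 6.2.1, and CSF is "analyzed by a validated method for the concentration of KM-819 (Part B only") under 6.2.3. Neither section describes an assay of unbound drug, so plasma Cmax is read here as total drug. Protocol 1.2.1.3 states: "In vitro plasma protein binding is 99.96 %, 99.79%, and 99.96% in rat, dog and human, respectively". No correction for binding and no reference value for the ratio appears in either document.

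Protocol Table 7-2 places CSF sampling before the first dose and 1 h after the last dose on Day 7. A plasma PK sample is also due at 1 h on Day 7. SAP 6.1.3 speaks of a single CSF sample per subject, which does not match that schedule.

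On values below the assay limit, SAP 6.3.12.2 says: "Values that are BLQ will be substituted with zero for the calculation of descriptive" statistics by time point. The same sentence then says they are shown as not calculable (NC) in statistical summaries. That section names neither CSF nor the ratio. SAP 6.3.13 has no BLQ rule, and the CSF limit of quantification (LLOQ) is not stated.

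CSF concentration is a separate PK endpoint. The SAP lists it by subject (Listing 16.2.6.3), and Protocol 8.7 also says it will be summarised by dose level and time point.

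**The concern.** KM-819 is meant to act on dopaminergic neurons, and the Part B schedule includes two lumbar punctures per subject. A CSF-to-plasma ratio is usually read against 1. With total plasma drug below the line and 99.96% of it bound, the ratio mainly reflects plasma binding and stays near zero whatever the penetration. Pairing a 1 h CSF sample with a Cmax reached at another time adds variation that has nothing to do with CNS entry.

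Expected CSF levels are also low enough that censoring is a live possibility. If a programmer carried the zero rule into the ratio, a censored result would become an exact 0. The protocol says data from this study will guide later dosing, so a misread ratio could count against a drug that does reach the CSF.

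**Working it through.** **Inputs.** Protocol 5.3 gives "CL= 2.93 L/h, V = 39.2 L, and half-life =9.27 hours", a one-compartment model with first-order absorption, and bioavailability F = 0.35. Part B doses are 30, 100, 200 and 400 mg once daily for 7 days. Binding of 99.96% gives fu = 1 - 0.9996 = 0.0004 (0.00035 to 0.00045 from rounding alone).

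**Assumptions.** The absorption rate ka is not given, so 0.3, 1 and 3 per h are used. Full equilibration is taken to mean CSF = fu x total plasma at the same time.

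**1. Reproduce the plan's figure.** k = 2.93/39.2 = 0.0747 per h, and ln 2/k = 9.27 h, which matches the stated half-life.

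**2. Ceiling at full equilibration.** If CSF equalled unbound Cmax, the planned ratio would be fu = 0.0004, which is 1/0.0004 = 2,500-fold below 1.

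**3. Day 7 plasma profile.** C(t) is the sum over i = 0 to 6 of F x D x ka / (V(ka - k)) x [exp(-k(t + 24i)) - exp(-ka(t + 24i))]. For 400 mg and ka = 1:
- The leading term is 0.35 x 400 / (39.2 x 0.9253) = 3.86 mg/L.
- The bracket at 1 h sums to 0.928 x 1.1995 - 0.368 = 0.745.
- C(1 h) is therefore 2,877 ng/mL.

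**4. Planned ratio with CSF at 1 h.** The table is for 400 mg. The ratio is the same at every dose because the model is linear.

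| ka (per h) | Cmax (ng/mL) | tmax (h) | C(1 h) (ng/mL) | fu x C(1 h) / Cmax | C(1 h) / Cmax |
|---|---|---|---|---|---|
| 0.3 | 2,869 | 5.37 | 1,768 | 0.000247 | 0.62 |
| 1 | 3,526 | 2.61 | 2,877 | 0.000326 | 0.82 |
| 3 | 3,916 | 1.20 | 3,895 | 0.000398 | 0.99 |

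At identical penetration, the timing mismatch alone moves the ratio by a factor of 0.000398/0.000247 = 1.6. The last column shows that dividing by fu x Cmax would not put full equilibration at 1 either.

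**5. CSF at 1 h on Day 7 at full equilibration (ng/mL), fu = 0.0004.**

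| Dose (mg) | ka 0.3 | ka 1 | ka 3 |
|---|---|---|---|
| 30 | 0.053 | 0.086 | 0.117 |
| 100 | 0.177 | 0.288 | 0.390 |
| 200 | 0.354 | 0.575 | 0.779 |
| 400 | 0.707 | 1.151 | 1.558 |

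Even at the Cmax of 9.3 ug/mL in the PK stopping criteria, unbound drug would be 9,300 x 0.0004 = 3.7 ng/mL.

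**6. Doses below an assumed LLOQ, despite full equilibration.**

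| LLOQ (ng/mL) | BLQ at every ka | BLQ at some ka |
|---|---|---|
| 0.05 | none | none |
| 0.5 | 30, 100 mg | 200 mg (ka 0.3) |
| 1 | 30, 100, 200 mg | 400 mg (ka 0.3) |
| 2 | all four | - |

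The 0.05 row is close: at fu = 0.00035 the lowest 30 mg value would be 133 x 0.00035 = 0.047 ng/mL. These are typical profiles without between-subject variation.

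**7. Upper bound compared with zero.** Take 400 mg, ka = 1 and an assumed LLOQ of 2 ng/mL. A censored planned ratio is below 2/3,526 = 0.00057. On the unbound, time-matched scale it is below 2/(0.0004 x 2,877) = 1.74. The data would then be compatible with full equilibration, whereas a reported 0 would suggest none.

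**The case against.** The ratio is descriptive. No threshold or test is attached to it, SAP 6.3.13.1 plans no formal PD analysis, and exploratory PD data do not enter the Part A escalation review. Dividing by a constant fu multiplies every value by 2,500, adds no data and leaves comparisons between doses unchanged. The study report could do it without a change to the SAP. All of this stands and limits the weight of the point. It does not cover the timing mismatch, which is not a constant, or the missing BLQ rule.

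A reader might infer three stronger things that the documents do not support:

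- **That the ratio is the only CNS-exposure measure.** CSF concentration is its own endpoint and is listed by subject. The ratio is only the sole plasma-normalised measure.
- **That the SAP orders zero for CSF or for the ratio.** The zero rule concerns concentrations by time point, and the SAP's concentration summary tables are for plasma. Its sentence also says NC, and listings show BLQ. SAP 6.3.4 says other data are reported as observed. The handling of the ratio is unstated: 0, NC and missing are all possible readings.
- **That full penetration will be reported as none.** That depends on an LLOQ the documents do not give, and at 0.05 ng/mL every dose would be quantifiable.

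**Conclusion.** The point holds in a limited form. The planned ratio would be about 0.00025 to 0.0004 if CSF fully equalled unbound plasma, and nothing in either document tells a reader so. The ceiling of about 0.0004 for CSF at or below unbound Cmax needs only the stated binding and the reading of plasma Cmax as total drug. The lower end rests on the protocol's predicted pharmacokinetics and an assumed ka of 0.3 to 3 per h.

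The BLQ gap is real, but its effect cannot be settled from the documents. It ranges from no dose affected (LLOQ 0.05 ng/mL) to all four (2 ng/mL). Observed human pharmacokinetics may differ from the prediction. The assumption that CSF tracks unbound plasma without delay at 1 h is also unverified. This is a cheap improvement to a descriptive secondary measure.

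**What to change.** In SAP 6.3.13 and Table 14.2.14:

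- Keep the planned ratio, with a note that it uses total plasma drug.
- Add, for Day 7 only, CSF(1 h) / (fu x plasma(1 h)), using the 1 h Day 7 plasma PK sample already scheduled. Under the equilibration assumption, 1 then means full equilibration.
- Use fu = 0.0004 and show results at 0.00035 and 0.00045, which reflect rounding alone. Label any wider range as an assumption.
- Drop change from baseline for the ratio, since a predose Day 1 CSF sample has no matching plasma Cmax. Reconcile the number of CSF samples in SAP 6.1.3 with Protocol Table 7-2.

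In SAP 6.3.12.2 and 6.3.13, for post-dose CSF in subjects on active drug:

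- Show a BLQ CSF value as <LLOQ, with the LLOQ stated.
- Give the ratio as an upper bound, not zero: LLOQ/Cmax for the planned ratio and LLOQ/(fu x plasma(1 h)) for the added one.
- Report the number of BLQ results per cohort.

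Compare the CSF LLOQ with the expected 0.05 to 1.6 ng/mL, so that the report can say what a BLQ result does and does not exclude.

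The cost is SAP wording and a derived variable; no new samples are needed. The downside is that fu is a single in vitro value, so the unbound ratio is approximate and should be presented that way.

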6.3.13.1 Statistical Analysis (Pharmacodynamic Analysis)

No formal statistical analysis is planned for the study.

6.3.14 Pharmacokinetic/Pharmacodynamic Analysis

No formal PK/PD statistical analysis will be performed for the study. Relationship between Pharmacokinetics and Pharmacodynamics parameters are assessed graphically.

PD parameters (Part A and Part B): Bond and Lader Visual Analogue Scale (VAS), Profile of Mood States (POMS) Korean Wechsler Adult Intelligence Scale-IV (K-WAIS-IV); Part B only: alpha synuclein oligomer, total Tau phospho-Tau) will be plotted vs PK parameters (AUCinf, AUClast and Cmax) [Figure 14.4.1.1 (Part A), Figure 14.4.1.2(Part B) , Figure 14.4.2.1 (Part A), Figure 14.4.2.2(Part B), Figure 14.4.3.1 (Part A), Figure 14.4.3.2(Part B), Figure 14.4.4 (Part B), Figure 14.4.5 (Part B), 14.4.6 (Part B)] with in each study part, by cohorts and nominal time point.

PAREXEL International
Statistical Analysis Plan

6.3.15 Safety Analysis

The analysis of the safety variables will be based on the safety population.

Safety will be assessed based on reported AEs, clinical laboratory assessments, vital signs measurements, 12-lead ECGs, and abnormal findings from physical examination.

Safety data will be summarized using descriptive statistics (n, mean, SD, minimum, median and maximum) will be reported within each study part and by cohort and time point and will include both absolute values and changes from baseline.

Categorical data will be summarized using frequencies and percentages will be reported within each study part, and by cohort.

6.3.15.1 Adverse Events

The following listings will be produced:

- All AEs. [Listing 16.2.7.1 (Part A) and Listing 16.2.7.2 (Part B)]:
- Withdrawals due to AEs [Listing 14.3.2.2.1 (Part A) and Listing 14.3.2.2.2 (Part B)]
- SAEs. [Listing 14.3.2.3.1 (Part A) and Listing 14.3.2.3.2 (Part B)]

A treatment-emergent AE (TEAE) will be defined as an AE that begins or that worsens in severity after at least one dose of study drug has been administered.

The following information will be included in the AE listing [Listing 16.2.7.1 (Part A) and Listing 16.2.7.2 (Part B)]: Verbatim, MedDRA lower level term (LLT), preferred term (PT), system organ class (SOC), AE onset date (and time) and study day, AE end date (and time) and duration (days), Concomitant Medication Administered, Related to Medical history condition, relationship to IMP, AE outcome, severity, AE ongoing and SAE indicator flag.

A table of summary of Treatment Emergent Adverse Events [Table 14.3.1.1.1 (Part A) and Table 14.3.1.1.2 (Part B)]; A table of number and percentage of subjects with AEs summarized by SOC, PT [Table 14.3.1.2.1 (Part A) and Table 14.3.1.2.2 (Part B)]; SOC, PT and severity [Table 14.3.1.4.1 (Part A) and Table 14.3.1.4.2 (Part B)]; SOC, PT and maximum severity [Table 14.3.1.5.1 (Part A) and Table 14.3.1.5.2 (Part B)] will be presented for each study part and also the number (percentage) of subjects with AEs summarized by SOC, PT, and relationship [Table 14.3.1.3.1 (Part A) and Table

PAREXEL International
Statistical Analysis Plan

14.3.1.3.2 (Part B)] to IMP. In the case of multiple occurrences of the same AEs (at the same preferred term level) in an individual patient, the AE with the greatest severity will be reported.

Serious AE, if any occur, will be summarized.

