**Table 6-1: Causal Relationship of Adverse Event to Study Drug**

Causal relationship	Description
Definite	A clinical event with a plausible time relationship to drug administration and which cannot be explained by concurrent disease or other drugs or chemicals. Response to withdrawal plausible (pharmacologically, pathologically), Event definitive pharmacologically or phenomenologically (i.e., an objective and specific medical disorder or a recognized pharmacological phenomenon), Rechallenge satisfactory, if necessary.
Probable	A clinical event with a reasonable time relationship to drug administration is unlikely to be attributed to concurrent disease or other drugs or chemicals. Response to withdrawal clinically reasonable (Rechallenge not required).
Possible	A clinical event with a reasonable time relationship to drug administration, but which could also be explained by concurrent disease or other drugs or chemicals.
Unlikely	A clinical event whose time relationship to drug administration makes a causal connection improbable, which could be plausibly explained by underlying disease or other drugs or chemicals.
Not related	A clinical event with no time relationship to drug administration, or with no causal relationship to drug administration (e.g., definitely induced by the clinical conditions of the subject or by the test procedures/requirements or by external events which are not associated with study treatments).
Unassessable	A clinical event with insufficient or contradictory information to permit assessment and identification of the cause.

The causal relationship of definite, probable, possible and unassessable will be considered as related to study drug.

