6. Screening height and weight will be used for BMI calculation for assessment of eligibility.
7. Blood will be tested for HBsAg, anti-HAV IgM, anti-HCV Ab, and anti-HIV Ab.
8. All hematology and serum chemistry labs will be taken after fasting for a minimum of 8 hours.
9. Simple spine X-ray examination will only be conducted at Screening for healthy elderly cohort.
10. Plasma samples for pharmacokinetics of KM-819 will be obtained on Day 1 predose (within 30 minutes prior to study drug administration) and 0.25, 0.5, 1, 2, 4, 6, 8, and 12 hours postdose, predose on Days 2, 3, 4, 5, 6,

---

and on Day 7 predose (within 30 minutes prior to study drug administration) and 0.25, 0.5, 1, 2, 4, 6, 8, 12, and 24 hours postdose.

11. CSF samples for pharmacokinetic of KM-819 will be obtained on Day 1 (at -120 minutes to 0 minute prior to the first dosing) and on Day 7 (at 1 hour after last dosing).
12. CSF samples for pharmacodynamic of KM-819 will be obtained on Day 1 (at -120 minutes to 0 minute prior to the first dosing) and on Day 7 (at 1 hour after last dosing).
13. Plasma samples for pharmacodynamic of KM-819 will be obtained on Day 1 (within 30 minutes prior to study drug administration) and on Day 7 (at 1 hour after last dosing).
14. Bond and Lader VAS, POMS, and K-WAIS-IV will be performed on Day -1, on Day 1 and Day 7 at predose, 3, 6, 12, and 24 hours postdose ( $\pm$  30 minutes for each time point).
15. The version of the C-SSRS to be performed at Screening is the “Baseline-Screening for Phase 1,” and the version of the C-SSRS to be performed on Day 3 and Day 8 (or at ED) is the “Since Last Visit”.

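### SAP 6.3.15.1 selects repeated adverse events by severity only, which leaves the relationship tables with an unsuitable rule or with none

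*SAP*

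**What the plan says.** SAP 6.3.15.1 lists the tables of treatment-emergent AEs (TEAEs): an overall summary, then system organ class (SOC) and preferred term (14.3.1.2.x), severity (14.3.1.4.x) and maximum severity, the last cited as "SOC, PT and maximum severity [Table 14.3.1.5.1 (Part A) and Table 14.3.1.5.2 (Part B"). The paragraph ends its list with the relationship tables, 14.3.1.3.1 and 14.3.1.3.2: "also the number (percentage) of subjects with AEs summarized by SOC, PT, and relationship" to study drug. These tables count subjects, not events.

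The next sentence of the same paragraph gives the handling of repeats. It opens "In the case of multiple occurrences of the same AEs (at the same preferred term level") and concludes "in an individual patient, the AE with the greatest severity will be reported". No table is named.

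Two other places bear on the point, and neither supplies a rule for repeats:

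- Protocol 8.6.1 asks for summaries by intensity and by causality.
- SAP 6.3.4 covers only unknown values: unknown severity is tabulated as severe, unknown causality as related.

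Protocol Table 6-1 has six causality categories. The text below it treats definite, probable, possible and unassessable as related.

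**The concern.** Intensity and causality are separate assessments (Protocol 6.4.1.3.2 and 6.4.1.3.3). Selecting a subject's event by intensity and then tabulating its causality can put the subject in the wrong row. Suppose a subject on KM-819 has a mild AE judged possibly related, and later a moderate AE of the same preferred term judged not related. Followed literally, the rule picks the moderate event and the subject appears only under not related.

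The relationship tables are the planned tabulation of causality in a study whose primary objective is safety and tolerability, and each active cohort has six subjects. At that size, one subject in the wrong row visibly changes a percentage.

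**Working it through.** The plan states no figure on this point, so there is none to reproduce. The check is a search of the text, an enumeration and simple fractions.

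**Inputs**

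- Three intensity grades: Protocol 6.4.1.3.2.
- Six causality categories, four of them related: Protocol Table 6-1.
- 6 active and 2 placebo subjects per cohort: SAP 5 and Protocol 4.5.2.
- 6 cohorts in Part A and 5 in Part B, elderly cohorts included: Protocol Tables 3-1 and 3-2.
- Placebo subjects shown as a pooled group: SAP 6.3.1.

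**1. Other rules.** Neither document gives another rule for repeated AEs in one subject.

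**2. Every severity pairing.** Take one related and one unrelated AE of the same term in one subject. The cells show what the greatest-severity rule does to the related event in the relationship table.

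| Related AE | Unrelated mild | Unrelated moderate | Unrelated severe |
|---|---|---|---|
| Mild | undefined (tie) | dropped | dropped |
| Moderate | kept | undefined (tie) | dropped |
| Severe | kept | kept | undefined (tie) |

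Of 9 pairings, 3 are kept, 3 dropped and 3 undefined. These are counts of pairings, not probabilities. SAP 6.3.4 adds to the dropped cases: an unrelated AE of unknown severity is tabulated as severe and so outranks a mild or moderate related AE.

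**3. Direction.** For a given term, let R(sev) be the number of subjects whose selected event is related, and R(any) the number with at least one related event. A related selected event implies at least one related event, so R(sev) ≤ R(any) however ties are broken. This holds for the related total. Single rows can move either way; the not-related row, for instance, gains the subject.

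**4. Size for one affected subject and one term.**

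- Active cohort: 0/6 (0.0%) under the SAP rule against 1/6 = 16.7% under a strongest-relationship count.
- Pooled placebo, Part A: 6 × 2 = 12, so 0% against 1/12 = 8.3%.
- Pooled placebo, Part B: 5 × 2 = 10, so 0% against 1/10 = 10.0%.

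These denominators assume full cohorts, no replacements, and placebo pooled over all cohorts of a part.

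**5. The narrower reading.** If the rule governed every table, 14.3.1.4.x and 14.3.1.5.x would be the same at preferred-term level, because each subject would enter both at the greatest severity. Planning both suggests that the rule may have been meant only for 14.3.1.5.x. In that case nothing says how a subject with a related and an unrelated AE of the same term enters 14.3.1.3.x.

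**The case against.** The strongest reply is about scope. The sentence names no table, and the duplication shown in step 5 points to a narrower intent. That stands: that the rule covers the relationship tables is inferred from its position and lack of restriction. It does not remove the problem, because on the narrower reading those tables have no rule.

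The second reply is that little depends on these tables. This also largely stands:

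- "All AEs. [Listing 16.2.7.1 (Part A) and Listing 16.2.7.2 (Part B") are planned with severity and relationship for each event, and the subject still counts in the SOC and preferred-term tables, so nothing is lost from the record.
- The stopping rules in Protocol 3.5 rest on investigator and sponsor judgement and on unblinding, not on these tables.
- Safety is summarised descriptively, and the AE endpoint in Protocol 3.2.1 does not name causality, although Protocol 8.6.1 requires a causality summary.

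The listings do not, however, correct a percentage that is wrong in the table.

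A reader might also infer that Part B makes the clash likely. Subjects have lumbar punctures on two days ("CSF samples for pharmacodynamic of KM-819 will be obtained on Day 1" before dosing, and again on Day 7), and Table 6-1 places events definitely induced "by the test procedures/requirements or by external events" under not related. The documents do not support a likelihood. They give no rate of puncture headache or of drug-related headache, and nothing shows that the two would be coded to the same preferred term. A headache that starts after the predose puncture but before dosing is not a TEAE unless it worsens after dosing. Placebo subjects follow the same schedule and the same rule, so no effect on the comparison with placebo can be derived either.

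**Conclusion.** The point holds as a gap in the counting rules. Read as written, SAP 6.3.15.1 removes a subject from the related count for a term whenever that subject's related AE is milder than an unrelated AE of the same term. It also leaves equal-severity cases undefined. Read narrowly, it leaves the relationship tables without a rule. Either way the SAP needs one.

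The direction needs no assumption: against a strongest-relationship count, related totals can only fall or stay the same. The size per affected subject follows from the planned denominators: 16.7 points in an active cohort, 8.3 or 10.0 points in pooled placebo. How many subjects would be affected cannot be estimated from the documents, so 16.7 points is the effect of one hypothetical subject and not an expected bias.

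A reader might conclude that drug-related AEs would be hidden from the study report, or that dose decisions would be affected. Neither follows, given the full listings and the basis of the stopping rules. This is a reporting correction of moderate-to-low severity.

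**What to change.** In SAP 6.3.15.1:

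1. Limit the greatest-severity rule to the maximum-severity tables (14.3.1.5.1 and 14.3.1.5.2), and say how the plain severity tables (14.3.1.4.x) count repeats, so that the two sets differ by design.
2. State that in Tables 14.3.1.3.1 and 14.3.1.3.2 each subject is counted once per preferred term and once per SOC, at the strongest relationship, whatever the severity. This also settles the ties.
3. Pre-specify an order of all six Table 6-1 categories in which definite, probable, possible and unassessable rank above unlikely and not related. One order that meets this is definite, probable, possible, unassessable, unlikely, not related. The place of unassessable among the first four is for the sponsor to set.

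The cost is about one SAP sentence and minor programming. Related-AE counts may become slightly less favourable. The change belongs before database lock, because the SAP sends later deviations to an addendum, where a change to related-AE counts could look data-driven.
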